1 PROTOCOL SUMMARY

1.1 SYNOPSIS

Title: TRANScranial direct current stimulation for PPost-stroke motor Recovery- a phase II sTudy (TRANSPORT2)

Study Description: TRANSPORT2 is a phase II multi-center transcranial direct current stimulation (tDCS) dosing selection study based on the preliminary efficacy, safety, tolerability and feasibility.

Objectives: **Primary Objective:** To determine whether there is an overall treatment effect among 3 dosing groups (sham+mCIMT, 2 mA+mCIMT, and 4 mA+mCIMT) on day 15 (\pm 2 days) after the start of the intervention in the Fugl-Meyer Upper-Extremity (FM-UE) scale, a measure of motor impairment. Additional outcome measures include the Wolf-Motor-Function-Test (WMFT), a measure of functional motor activity, and the Stroke-Impact-Scale (SIS), a measure of quality of life. Sustained benefit will be assessed at day 45 (\pm 5 days) and day 105 (\pm 10 days).

Secondary Objectives: To confirm that the proposed intervention is safe (no significant differences in rate of adverse events), tolerable (no significant differences in discomfort as measured by Visual-Analog-Scale), and feasible to administer in a multi-site trial (>80% of subjects complete the treatment protocol and no unexplained/unresolved variability by site).

Exploratory Objectives: To examine whether wCST-LL (structural assessment of integrity of descending motor tract) or MEPs (functional assessment of integrity of descending motor tract) or combination of both are correlated with changes in FM-UE scale, and evaluate the utility of these measures as biomarkers for patient selection criteria in the future confirmatory Phase III study. We also

aim to examine whether structural and functional changes within descending motor tracts correlate with changes in motor impairment and functional motor activity.

Endpoints:

Primary Endpoint: Fugl-Meyer Upper-Extremity (FM-UE) scale a measure of motor impairment;

Secondary Endpoints: Wolf Motor Function Test (WMFT) time score, a measure of functional motor activity; Stroke-Impact-Scale hand subscale as an assessment of patient-centered quality of life.

Study Population:

Subject who is 18-80 years of age of any gender or ethnicity, who had first-ever unihemispheric ischemic stroke in past 30-180 days resulting in unilateral limb weakness with FM-UE ≤ 54 (out of 66) that is stable across two baseline visits at the time of randomization and an mRS ≤ 2 pre-stroke. We are planning to enroll 129 subjects across three arms.

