1.3 SCHEDULE OF ACTIVITIES (SOA)

Event	Baseline 1	Baseline 2 ³ –	Treatment Sessions (1-10)	Follow Up 1	Follow Up 2	Follow Up 3	End of Study
	Day -20 to -7	Day -6 to 1		Day 15 ±2	Day 45 ±5	Day 105 ±10	
Informed Consent	X						
Inclusion/Exclusion ¹	X						
Demographics	X						
Montreal Cognitive Assessment (MOCA)	X						
Medical and Social History (Including Pre-Stroke Modified Rankin Scale (mRS))	X						
Medication Checklist	X	X					
Vital signs	X						
Fugl-Meyer Assessment– Upper Extremity Scale	X	X		X	X	X	
NIH Stroke Scale (NIHSS)		X					
Transcranial Magnetic Stimulation (TMS)		X ¹		X			
Randomization			X ²				
tDCS Treatment Activation Code Request (Retrieved at beginning of every Treatment Session)			X				
tDCS Questionnaires (Pre-Stimulation, Post-Stimulation, Post mCIMT)			X				
tDCS			X				
Modified Constraint Induced Movement Therapy (mCIMT)			X				
Wolf Motor Function Test (WMFT)		X		X	X	X	
Stroke Impact Scale (SIS)		X		X	X	X	
MRI		X ¹		X			
Concomitant Therapy				X	X	X	
Blindedness Assessment			X ⁴				
Visual Analog Scale			X ⁴				
End of Study							X

1. A urine pregnancy test for all women of child-bearing potential will be given at this visit.

2. Randomization ONLY occurs at 1st Treatment Session

3. This visit can be broken up over several days. All baseline activities need to take place prior to Day 1 treatment activities. Please see MOP and FAQs for more details on this visit.

4. End of Treatment ONLY occurs at Final Treatment Session

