7 STUDY INTERVENTION DISCONTINUATION AND SUBJECT DISCONTINUATION/WITHDRAWAL

7.1 DISCONTINUATION OF STUDY INTERVENTION

Discontinuation from tDCS and mCIMT intervention does not mean discontinuation from the study, and remaining study outcome assessments should be completed as indicated by the study protocol. If a clinically significant finding is identified (including, but not limited to changes from baseline) after enrollment, the investigator or qualified designee will determine if any change in subject management is needed. Any new clinically relevant finding will be reported as an adverse event (AE). An investigator may discontinue or withdraw a subject from study intervention for the following reasons:

- Pregnancy, but it is unlikely as woman of child-bearing potential will have urine pregnancy test to confirm or exclude the possibility of a pregnancy.
- Significant study intervention non-compliance, defined as missing >2 sessions out of 10 sessions and unable to make it up within the 2 week/14 days intervention period;
- If any adverse event (AE), laboratory abnormality, other medical condition or situation occurs such that continued participation in the study intervention would not be in the best interest of the subject.
- Disease progression (e.g., 4 points or more increases in the NIHSS score or recurrent stroke) which requires discontinuation of the study intervention.
- If a subject meets an exclusion criterion (either newly developed or not previously recognized) that precludes further study participation.
- Subject suffers another stroke, neurological or neuromuscular disease during the study period that may have an impact on motor recovery.

The reason for intervention discontinuation from the study will be recorded on the Case Report Form (CRF). The subject should continue to be followed and have all study assessments.

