9.4.4 SAFETY ANALYSES

Safety: Analysis Method

IMSM and Data and Safety Monitoring Board (DSMB) will receive periodic safety reports of all reportable adverse events including serious adverse events (SAEs) if there are any. All clinical safety endpoints and SAEs will be summarized by AE code (as provided on the AE CRF) regarding the frequency of the event, the number of subjects having the event, severity, and relatedness to the study treatment. Clinically important adverse events include:

- Severe headache
- Second-degree skin burn
- Clinical seizure
- Neurological deterioration (\geq 4-point increase in NIHSS)

The proportion of subjects experiencing each of these events will be provided in the closed report by intervention arm with two-sided 95% CIs and unadjusted relative risks. Based on the Phase I dose-escalation study, no subjects experienced any of the clinically important adverse events. Fisher's exact tests will be used to assess intervention group differences in the rates of clinically important adverse events.

Tolerability: Analysis Method

Tolerability will primarily be measured through the use of the Visual-Analog scale (VAS), a 10-point scale ranging from 0 (No Discomfort) to 10 (Extreme Discomfort). For the primary analysis, any subject who requests to be withdrawn from the study due to procedure related issues will be imputed as a 10 on the Visual-Analog Scale. Differences in tolerability will be assessed using a Kruskal-Wallis test at a 10% type-I error rate.

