10.4 PROTOCOL AMENDMENT HISTORY

Version	Date	Description of Change	Brief Rationale
5	11/9/20	Version and Date Update on Title Page	
5	11/9/20	Update number of sites to 15 throughout protocol	3 additional sites were added to original 12
5	11/9/20	Clarified schema and schedule of activities 1 st qualifying baseline days -20 through -7 and 2 nd qualifying baseline days -6 through 1	Clarification
5	11/9/20	Added that baseline visit 2 can be broken up over several days. All baseline activities need to take place prior to treatment visit activities start.	Clarification
5	11/9/20	Superscript 4 in schedule of activities denotes an activity that only takes place at final treatment session.	Clarification
5	11/9/20	30 minute dose of tDCS updated to include (\pm 6) minute window throughout	Although variation unlikely it is possible due to interruption and technical variation, a deviation of less than 20% (24-36 minutes) is considered within the tolerated window of receiving a full dose
5	11/9/20	120 minute dose of mCIMT updated to include (\pm 24) minute window throughout protocol	Although variation unlikely it is possible due to interruption and technical variation, a deviation of less than 20% (96- 144 minutes) is considered within the tolerated window of receiving a full dose
5	11/9/20	Phone screen was updated to prescreen interview throughout protocol	Allows for the use of video for prescreening
5	11/9/20	Updated the number of possible training subjects from 5 to 12	Staff changes have required more training subjects than originally thought
5	11/9/20	Removed randomization and generate a code corresponding to in the following sentence. tDCS will be executed by entering WebDCU-generated code in the computer, which will initiate one of the three interventions according to the group to which the subjects was randomized	Clarification
5	11/9/20	Added: On the randomization day, a study coordinator or a team member will log into WebDCU™ to randomize subjects who have been consented and found eligible. Briefly, at the beginning of each intervention session, the coordinator will complete tDCS Treatment Activation Code Request to obtain a new tDCS treatment activation code daily. Each day, the coordinator will need to enter the new code into the tDCS machine which will translate the code to the appropriate stimulation voltage using a pre-loaded script	Clarification

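### A subject who stops stimulation for procedure-related reasons but stays in follow-up has no clearly scheduled tolerability VAS and no imputed score

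*Combined protocol and SAP*

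**What the plan says.** - **Measure and test.** Section 9.4.4: "Tolerability will primarily be measured through the use of the Visual-Analog scale (VAS"), scored from 0 to 10. "Differences in tolerability will be assessed using a Kruskal-Wallis test at a 10% type-I error rate".
- **Criterion.** The synopsis (section 1.1) defines the intervention as "tolerable (no significant differences in discomfort as measured by Visual-Analog-Scale"). A non-significant result is the favourable one.
- **Timing.** The VAS row in section 1.3 carries footnote 4: "End of Treatment ONLY occurs at Final Treatment Session". The version 5 entry in section 10.4 explains the same mark: "Superscript 4 in schedule of activities denotes an activity that only takes place at final treatment session".
- **Missing scores.** The only rule is in section 9.4.4: "any subject who requests to be withdrawn from the study due to procedure related issues will be imputed as a 10".
- **Stopping treatment.** Section 7.1: "Discontinuation from tDCS and mCIMT intervention does not mean discontinuation from the study". After the reason for stopping is recorded, "The subject should continue to be followed and have all study assessments".
- **Other tolerability data.** A tDCS questionnaire is completed at every session (sections 1.3, 2.3.3 and 8.2), but the tolerability test in 9.4.4 does not use it.

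**The concern.** The score-of-10 rule shows that the authors meant intolerance to count as the worst outcome. They tied it to leaving the study at the subject's own request. The event that matters for tolerability is stopping stimulation, and section 7.1 makes that a separate state. It also lets the investigator stop the intervention for an adverse event, in which case the subject may have made no request at all.

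Take a subject who stops at session 3 because of burning under the electrode and then attends Days 15, 45 and 105. This subject complies with section 7.1, may have no VAS, and does not meet the condition for a 10. A Kruskal-Wallis test uses only observed or imputed scores, so without either the subject is left out. The missing value is then caused by the outcome being measured, and the better a site follows section 7.1, the more such subjects are affected.

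The trial is meant to help choose between 2 mA and 4 mA, and section 9.4.1 asks whether the higher dose keeps a similar tolerability profile. Because non-significance counts as success, losing high scores from one arm would favour a finding of tolerable.

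**Working it through.** **1. Tracing each kind of subject through the rules**

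| Subject | VAS scheduled? | Scored 10? |
|---|---|---|
| Completes treatment | Yes, final session | Not needed |
| Asks to leave the study for procedure-related issues | Not clearly | Yes (9.4.4) |
| Stops stimulation for procedure-related reasons, stays in follow-up | Not clearly | No |

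The third row is the gap. The intent-to-treat statement in section 9.3 puts every randomized subject in every analysis but supplies no score for a missing VAS.

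**2. Inputs from the documents**

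- Sample size (section 9.2): 31/(1 − 0.08)² = 36.6; 36.6 × 1.15 = 42.1, rounded up to 43 per arm. The stated 43 is reproduced.
- Incomplete treatment for any reason (section 9.2): 8%. 0.08 × 43 = 3.4 per arm. Those who stop for discomfort are some unknown part of these.
- Test: Kruskal-Wallis at 10%.
- The documents state no power for the tolerability comparison, no VAS distribution and no rate of stopping for discomfort. Everything below is therefore illustrative.

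**3. Simulation A: 4 mA truly less comfortable**

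Assumptions: 43 per arm; gamma scores with shape 1.5 and means 2 (sham), 2 (2 mA) and 3 (4 mA), rounded and limited to 0–10; within each arm the highest scorers stop. *As written* drops the stoppers; the alternative scores them 10. Entries are the chance of p < 0.10, with simulation error of about one percentage point. With no stoppers it is about 65%.

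| Stoppers (sham/2 mA/4 mA) | As written | Scored 10 |
|---|---|---|
| 0/0/1 | 60% | 67% |
| 0/0/2 | 55% | 67% |
| 0/0/3 | 47% | 68% |
| 0/0/4 | 39% | 66% |
| 1/1/2 | 62% | 66% |
| 2/3/5 | 54% | 63% |
| 3/3/3 | 70% | 60% |

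Three stoppers at 4 mA is close to the 3.4 per arm expected to have incomplete treatment for any reason. In the last row the direction reverses.

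**4. Simulation B: completers alike in all arms**

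Same test and arm size; gamma scores with shape 1.5 and scale 1.5 in every arm; the arms differ only in the number of stoppers.

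| Stoppers (sham/2 mA/4 mA) | As written | Scored 10 |
|---|---|---|
| 0/0/2 | 10% | 11% |
| 0/1/4 | 10% | 14% |
| 0/2/6 | 10% | 21% |

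As written, the rejection rate stays at the nominal 10% however unevenly the stoppers fall: the test cannot see a difference in stopping. With two stoppers the practical effect is negligible.

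**The case against.** Several points on the other side have force.

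- **The VAS may still be collected.** Footnote 4 does not say session 10. For an early stopper, the final treatment session can be read as the last one given, and section 7.1 asks for all study assessments to continue. This stands: a reader might infer that these subjects certainly have no VAS, and the text does not go that far. But it does not direct sites to take one either. Sites could differ, and a decision to stop made after a session would come too late for it.
- **The detail may sit elsewhere.** Section 9.4 refers to the Statistical Analysis Plan for details. The text available contains no separate rule for a missing VAS. If one exists, section 9.4.4 should point to it.
- **These subjects are not lost to the dose assessment.** Treatment completion is its own endpoint, reasons for stopping are recorded, adverse events are collected during the intervention, and severe headache and second-degree burns are compared by arm. This stands. The exposure is one secondary test and the conclusion drawn from it.
- **Few may stop for discomfort.** Section 2.2 reports no discontinuations in the phase I study of doses up to 4 mA, and the 8% planning figure covers all reasons. Counts above about three at 4 mA alone exceed that planning figure, so larger ones are extreme scenarios.
- **A score of 10 is a choice, not a measurement.** It can overstate discomfort, and with even stopping it lowers the chance of detecting a difference. It is, however, the sponsor's own choice for those who leave the study. The question is why those who stop and stay are treated differently.

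**Conclusion.** The gap is real on the text. The worst-score rule is attached to leaving the study, while the protocol keeps in the study those who stop stimulation, without a clearly scheduled VAS or an imputed value for them.

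A reader might go further and infer that the Kruskal-Wallis test is biased towards no difference in every case. The documents do not support that. The direction depends on procedure-related stopping being commoner at 4 mA, which is plausible but nowhere stated; with even stopping the bias is small or can reverse.

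The size is unknown. Under the assumptions of simulation A, with stoppers at 4 mA only, the loss in the chance of a significant result runs from 7 percentage points with one stopper (67 − 60) to 27 with four (66 − 39). It rests on an assumed score distribution, an assumed one-point difference in means and the highest scorers being those who stop. Severity is moderate: a secondary objective is affected, and the primary endpoint is not.

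**What to change.** 1. **Section 9.4.4 and the SAP.** Extend the existing score of 10 to any subject whose stimulation is discontinued for procedure-related reasons, whether or not the subject leaves the study and whoever makes the decision. State that this value is used in the primary tolerability analysis.
2. **Section 1.3, footnote 4.** State that for a subject who stops early the VAS is taken at the last session attended or at the discontinuation contact. Use the measured score for subjects who stop for other reasons, and in a sensitivity analysis that replaces the imputed 10.
3. **Reporting.** Give the number of procedure-related stoppers by arm beside the test result, with the per-session tDCS questionnaires as supportive data.

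The cost is a sentence or two in 9.4.4, one footnote and one extra analysis, with no new visit or instrument. The drawback is that a 10 may overstate discomfort for some stoppers, which the sensitivity analysis will show. The change should be made before unblinding, and the timing rule as early as possible, because an end-of-treatment VAS that was not taken cannot be recovered.

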9.4.5 BASELINE DESCRIPTIVE STATISTICS

The characteristic of subjects at baseline will be tabulated ordered by 3 dose groups. p value is based on ANOVA if the variable is continuous and is based on Chi-squared test if the variable is categorical.

9.4.6 SUB-GROUP ANALYSES

In pre-specified subgroup analyses, the primary analysis (§9.4.2) will be repeated but include an interaction effect between sex/gender or race/ethnicity and intervention arm. Differential effects of tDCS by sex/gender or race/ethnicity are not anticipated, and therefore the trial is not powered specifically for these subgroup analyses, but these subgroup analyses will allow any unexpected large variations to be identified and regardless of outcome will assist with planning a Phase III trial which will account for differences if identified here.

Additional analyses are specified in the statistical analysis plan (SAP).

9.4.7 TABULATION OF INDIVIDUAL PARTICIPANT DATA

Individual subject data will not be listed or tabulate by measure and time point. Only summarized data by dose group and time points and measures will be presented.

10 SUPPORTING DOCUMENTATION AND OPERATIONAL CONSIDERATIONS

10.1 REGULATORY, ETHICAL, AND STUDY OVERSIGHT CONSIDERATIONS

10.1.1 INFORMED CONSENT PROCESS

10.1.1.1 CONSENT/ASSENT AND OTHER INFORMATIONAL DOCUMENTS PROVIDED TO PARTICIPANTS

Consent forms describing in detail the study intervention, study procedures, and risks are given to the subject, and written documentation of informed consent is required prior to starting intervention/administering study intervention.

10.1.1.2 CONSENT PROCEDURES AND DOCUMENTATION

Informed consent is a process that is initiated prior to the individual's agreement to participate in the study and continues throughout the individual's study participation. Consent forms will be Institutional Review Board (IRB)-approved, and the subject will be asked to read and review the document. The investigator will explain the research study to the subject/LAR and answer any questions that may arise. A verbal explanation will be provided in terms suited to the subject's comprehension of the purposes, procedures, and potential risks of the study and their rights as research subjects. Subject/LAR will have the opportunity to carefully review the written consent form and ask questions before signing. Subject/LAR should have the opportunity to discuss the study with their family or surrogates or think about it prior to agreeing to participate. Subject/LAR will sign the informed consent document prior to any procedures being done specifically for the study. Subject who is cognitively capable will sign informed consent; If subject is unable to provide written informed consent due to cognitive impairment (e.g., NIH Stroke Scale Level of Cognition Questions 1-3 combined score ≥ 3), a Legally Authorized Representative (LAR) will sign informed consent instead. During the follow-up visit, subject who was initially cognitively impaired

will be reassessed his/her cognition by study team member, if subject regains cognitive capability, he/she will be given an opportunity to decide if he/she still wants to remain in the study. Subject/LAR must be informed that participation is voluntary and that they may withdraw from the study at any time, without prejudice. A copy of the informed consent document will be given to the subject/LAR for their records. The informed consent process will be conducted and documented in the source document (including the date), and the form signed before the subject undergoes any study-specific procedures. The rights and welfare of the subjects will be protected by emphasizing to them that the quality of their medical care will not be adversely affected if they decline to participate in this study.

In an effort to review informed consent forms in a timely manner, enrolling sites will upload a pdf of the signed informed consent form, into the password protected clinical trial management system, WebDCU™. The PDF file will be linked to the subject ID but will be stored on a secure server separate from the study's CRF data. The secure server on which these files are stored is not backed up to prevent copies of files containing individually identifiable health information from being copied and stored on non-NDMC back up servers. The files on these servers can only be accessed by designated NDMC study personnel. NDMC staff will remotely monitor the informed consent forms and issues identified will be relayed to the clinical site for corrective and preventative action. After remote monitoring is complete, the PDF file containing the informed consent form will be permanently deleted from the secure server. If a subject must be re-consented, the process will repeat itself.

10.1.2 STUDY DISCONTINUATION AND CLOSURE

This study may be temporarily suspended or prematurely terminated if there is sufficient reasonable cause. Written notification, documenting the reason for study suspension or termination, will be provided by the suspending or terminating party to study subjects, investigator, funding agency, and regulatory authorities if applicable. If the study is prematurely terminated or suspended, the Principal Investigator (PI) will promptly inform study subjects, the cIRB, and sponsor and will provide the reason(s) for the termination or suspension. Study subjects will be contacted, as applicable, and be informed of changes to study visit schedule.

Circumstances that may warrant termination or suspension include, but are not limited to:

- Determination of unexpected, significant, or unacceptable risk to subjects
- Demonstration of efficacy that would warrant stopping
- Insufficient compliance with protocol requirements
- Data that are not sufficiently complete and/or evaluable
- Determination that the primary endpoint has been met
- Determination of futility

The study may resume once concerns about safety, protocol compliance, and data quality are addressed, and satisfy the sponsor, and/or the cIRB.

